9.0 Research Methods

9.1 Study Design

This study is designed as a prospective, observational study to assess the effect of adalimumab on health-related QoL and work productivity in patients with RA in Taiwan in clinical practice.

Note: This study is non-interventional and the subjects/investigators will follow the current clinical practice in each site and also the routine clinical follow up as determine by the treating physician.

This study is non-interventional. Patient therapy is not decided by the study protocol but falls within current medical practice, and the prescription of adalimumab is clearly separated from the decision to include the patient in this study. The subjects/investigator will follow the current clinical practice in each site and also the routine clinical follow up as determine by the treating physician.

RA patients will be recruited from within the clinical settings of each rheumatologist participating in the study. Approximately 100 patients diagnosed with RA that meet the inclusion and exclusion criteria will be enrolled at approximately 7 sites in Taiwan.

To assess health and disability outcomes, the HAQ DI at baseline, Week 12 and Week 24 after treatment initiation with adalimumab will be collected. In addition, other PROs of work activity and well-being, including the WPAI, EQ-5D, and SF-36, will also be collected. All above instruments have been validated for the Chinese version.

The HCRU will also be collected. This includes surgical procedures, hospitalizations, bed days in hospital, physician consultations etc. Costs will be assigned based on the HCRU using standardized costs for each participating centers.

The patients identified by the recruiting investigators based on the study selection criteria will be collected data as observed on QoL, functioning, work productivity,

treatment satisfaction, impression of change and HCRU. Data will be captured at baseline (D0), Week 12 and Week 24.

Subjects may discontinue adalimumab treatment at any time during study participation. Subjects that end study participation early will have a Termination Visit, which may be a routine follow-up visit at investigator's clinic. All subjects will have a data recorded approximately 70 days after the Week 24 dosing or after the last administration of adalimumab to obtain information on any new or ongoing AEs.

Primary Endpoint Analysis

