9.2.6 Removal of Subjects from Therapy or Assessment

1. Discontinuation of Individual Subjects

A subject may withdraw from the study at any time. The Investigator may discontinue any subject's participation for any reason, including an adverse event, safety concerns or failure to comply with the protocol.

Subjects will be withdrawn from the study immediately if any one of the following occurs:

- Clinically significant abnormal laboratory result(s) or adverse event(s), as determined by the Investigator in consultation with the AbbVie Medical Monitor.
- The Investigator believes it is in the best interest of the subject.
- The subject requests withdrawal from the study.
- Inclusion and exclusion criteria violation was noted after the subject started study drug, when continuation of the study drug would place the subject at risk as determined by the AbbVie Medical Monitor (see *Section 5.2* and *Section 7.0*).
- Introduction of prohibited medications or dosages when continuation of adalimumab would place the subject at risk as determined by the AbbVie Medical Monitor.
- Subject is non-compliant with TB prophylaxis.
- The subject becomes pregnant during the study period.
- Subject has dysplasia of the gastrointestinal tract or a malignancy, except for localized non-melanoma skin cancer. Discontinuation for carcinoma in-situ of the cervix is at the discretion of the Investigator.
- Subject is diagnosed with lupus-like syndrome, multiple sclerosis or demyelinating disease.
- Subject is significantly non-compliant with clinical follow-up which would put the subject at risk for continued participation in the trial, as determined by the Investigator, in consultation with the AbbVie Medical Monitor.

The subject will be treated in accordance with the Investigator's best clinical judgment. If the subject prematurely dropped out from the study, the pre-defined Terminal Visit data should be collected within 2 weeks of the last dose of adalimumab, and preferably prior to the initiation of another therapy. However, these data collection should not interfere with the initiation of any new treatments or therapeutic modalities that the Investigator feels are necessary to treat the subject's condition. A final data of a subject will be recorded

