9.7.4 Primary Endpoint Analysis

The primary endpoint variable will be the change in HAQ DI score at 24 weeks after the initiation of adalimumab, in those patients continuing on adalimumab (as observed population).

The objective of the primary endpoint analysis will be to demonstrate that treatment with adalimumab improves functioning as measured by the HAQ DI in subjects with RA following treatment initiation. This change will be summarized as the mean and 95% confidence interval and will be tested with a paired t-test without adjusting for baseline disease severity. For sensitivity analysis, the mean change in HAQ DI at Week 24 will be analyzed using ANOVA adjusting for baseline disease severity.

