9.8.2 Quality Assurance

Prior to the initiation of the study, physician and site personnel will be trained on the study. Training will include a detailed discussion of the protocol, performance of study procedures, and completion of the CRFs and paper questionnaires.

All sites will be monitored during the course of study participation. One hundred percent (100%) source document review for safety will be performed.

All clinical data will be documented via the CRF. Study coordinators at each site will check the paper CRFs completed by the physicians and questionnaires completed by patients (e.g., all questions were answered). Data entry will be conducted by IMS. After entry of the data, computer logic checks will be run to check for inconsistent data. Any necessary corrections will be made to the database and documented via addenda, queries, and source data clarification forms.

Steps to be taken to ensure the accuracy and reliability of data include the selection of qualified investigators and appropriate study centers, review of protocol procedures with the investigator and associated personnel before the study and periodic monitoring visits by the sponsor. Written instructions will be provided for administration and collection of study questionnaires.

Guidelines for CRF completion will be provided and reviewed with study personnel before the start of the study. The sponsor will review CRFs and patient questionnaires for accuracy and completeness after transmission to the sponsor; any discrepancies will be resolved with the investigator or designee, as appropriate. After upload of the data into the clinical study database they will be verified for accuracy and consistency with the data sources.

Protocol Deviation

For the purposes of this protocol, reportable deviations are defined as:

- Subject entered into the study even though she/he did not satisfy entry criteria
- Subject who developed withdrawal criteria during the study and was not withdrawn
- Subject who received excluded or prohibited concomitant treatment

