By signing the investigator's confidentiality agreement, the investigator affirms to AbbVie/IMS that information furnished by AbbVie/IMS to the investigator will be kept in confidence and such information will be divulged to any expert committee, affiliated institution, and employees only under an appropriate understanding of confidentiality with such committee, affiliated institution and employees.

12.3 **Study administration**

The entire study will be managed by an international project coordinator at IMS Japan K.K. who will coordinate the project and maintain fluid communication with the study sponsor, the study team and the director at IMS Japan K.K.

As part of the monitoring plan, regular phone calls (at least every two weeks) will be made between IMS and local site coordinator in order to check inclusion status, resolve any issues, check data plausibility, etc.

12.4 **Investigators compliance**

By signing the investigator's agreement, the investigator agrees to conduct the study in an efficient and diligent manner and in conformance with this protocol, generally accepted standards of good clinical practice and all applicable laws, rules and regulations relating to the conduct of the study.

The investigator shall prepare and maintain complete and accurate study documentation in compliance with applicable national and local laws, rules and regulations and, for each patient participating in the study, promptly record all data in the CRF as required by this protocol.

12.5 **Risks**

This is a non-interventional observational study. It does not involve any direct patient intervention with respect to laboratory tests, examinations or drug treatment. Patients will be asked to complete questionnaires related to their RA, QoL, functioning, work productivity, treatment satisfaction, and healthcare resource utilization at their clinic during their visit three times over the course of 6 months, requiring approximately 30 minutes of their time each time.

12.6 **Discontinuation or Drop-out**

Patients' participation in the study is completely voluntary, and they are allowed to withdraw or discontinue from the study. The following three situations will be counted as study drop-out:

- 1) Patient is switched off Adalimumab
- 2) Patient is not willing to continue participation in the study
- 3) Patient disappears and cannot be contacted anymore

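### Section 9.2.6 can remove a patient from the study while still on adalimumab, and such a patient fits neither the drop-out list in 12.6 nor either analysis population

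*Protocol*

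**What the plan says.** **Withdrawal rule (Protocol 9.2.6).** "Subjects will be withdrawn from the study immediately if any one of the following occurs". Ten grounds follow. The first is "Clinically significant abnormal laboratory result(s) or adverse event(s), as determined by the Investigator in consultation with the AbbVie Medical Monitor", with no condition about whether the drug is stopped. Non-compliance with TB prophylaxis is also unconditioned. Two grounds do carry a condition tied to the drug. One is an eligibility violation found after treatment began. The other is "Introduction of prohibited medications or dosages when continuation of adalimumab would place the subject at risk as determined by the AbbVie Medical Monitor".

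**Force of the rule (Protocol 9.8.2).** Keeping a subject who has met a withdrawal criterion is a reportable deviation. So is "Subject who received excluded or prohibited concomitant treatment".

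**Drop-out (Protocol 12.6).** "The following three situations will be counted as study drop-out": switched off adalimumab, unwilling to go on, or no longer contactable. Nothing more is collected after drop-out except the reason. A patient who merely misses a questionnaire is not a drop-out.

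**Populations (Protocol 9.7.4 and 9.7.6; SAP 2.1, 2.3 and 5.3).** The primary analysis is the Week 24 HAQ-DI change in patients continuing on adalimumab (as observed). The withdrawal population is those not continuing on it.

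**Missing data (Protocol 9.7.9; SAP 3.5.5).** There is no imputation of outcomes beyond item level. The SAP adds that missingness cannot be taken as MCAR or MAR.

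**Setting (Protocol 9.1).** "Patient therapy is not decided by the study protocol but falls within current medical practice".

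**The concern.** The primary result is meant to describe patients who stay on adalimumab in routine care. A binding rule that ends study participation because of an adverse event or laboratory finding, without asking whether the drug was stopped, can take some of those patients out before Week 24. They would be lost because of something that happened to them on treatment, which is the kind of loss an available-case analysis handles badly. If their function improved less, the mean change and the proportion reaching the 0.22-point improvement would both look better than they are among all continuers. The plan would also have no place to report these patients, since they match neither of its two populations.

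**Working it through.** **Step 1. Can a patient be withdrawn while still on adalimumab?** Of the ten grounds in 9.2.6, one (the subject's own request) matches a 12.6 category by itself, and two (eligibility violation, prohibited medication) apply only when continuing the drug would put the subject at risk. That leaves 10 - 1 - 2 = 7 grounds with neither a drug-related condition nor a 12.6 category of their own. Since the authors wrote the drug condition into two grounds, its absence from the others carries some weight. The clinician's Early Termination Form (Appendix K) asks for a stop date and reason only if adalimumab was stopped, so termination on drug is foreseen. The reading is open on the text.

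**Step 2. Where does that patient go?**

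| Rule | Does the patient fit? |
|---|---|
| 12.6 drop-out | No: not switched off, not unwilling, not lost |
| As-observed, Week 24 (9.7.4) | On drug, but no Week 24 score after withdrawal |
| Withdrawal population (9.7.6, SAP 5.3) | No: still continuing adalimumab |
| Imputation (9.7.9, SAP 3.5.5) | None beyond item level |
| Early-termination HAQ (Table 1) | Collected, but no planned analysis places it for this patient |

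**Step 3. The plan's own power figure.** Inputs from Protocol 9.5: 100 patients, 10% dropout, two-sided 0.05. So n = 100 × 0.90 = 90.
- Against 0: noncentrality 0.21/0.5 × √90 = 3.98, paired t-test power 97.6%.
- Against -0.22: (0.50 - 0.22)/0.7 × √90 = 3.79, power 96.4%.

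Both agree with the stated figure of at least 95%.

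**Step 4. Size of the bias.** Let k be the share of continuing patients removed and d their mean change minus that of the retained patients (positive means worse). The mean over all continuers is (1 - k) × retained + k × (retained + d) = retained + k × d. The retained mean is therefore too favourable by k × d.

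Neither k nor d is in the documents. The assumed ranges are k = 3–10% (about 3 to 9 of 90 patients) and d = 0.2–0.5.

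| k | d | k × d | Share of 0.21 |
|---|---|---|---|
| 3% | 0.2 | 0.006 | 2.9% |
| 3% | 0.5 | 0.015 | 7.1% |
| 10% | 0.2 | 0.020 | 9.5% |
| 10% | 0.5 | 0.050 | 23.8% |

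**Step 5. Bias or power?** At k = 10%, n = 90 × 0.90 = 81 and power is 96.2% against 0 and 94.5% against -0.22, so little is lost. With SD 0.5 and no true change among all continuers, the chance of declaring improvement rises from the nominal 2.5% to 5.6% for d = 0.21 and 14.2% for d = 0.50, again at k = 10%. What matters is bias, and only if k and d are near the top of the assumed range.

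**The case against.** The strongest reply is that 9.2.6 mostly presumes that leaving the study and stopping the drug go together. Its heading covers removal from therapy or assessment, and its Terminal Visit is timed from the last dose, preferably before another therapy starts. Patients who stop adalimumab are outside the as-observed population by definition, so 9.2.6 adds no bias for them. This stands, and it limits the problem to patients withdrawn while still on drug, whose number may be small.

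The adverse-event ground also depends on the investigator's judgment in consultation with the Medical Monitor, so not every event in a continuing patient triggers it. That stands too. Data are not wholly lost either: Table 1 has HAQ at early termination, and a completed Week 12 score still enters the Week 12 analysis.

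On size, 0.05 is slightly below one standard error of the planned mean (0.5/√90 = 0.053), and reaching it needs extra removals as large as the whole planned dropout rate. Nothing in the documents shows that the removed patients do worse.

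Two stronger readings are tempting, and neither is supported. A reader might infer that continuing patients are removed for added medication, but that ground applies only when "Introduction of prohibited medications or dosages when continuation of adalimumab would place the subject at risk". A reader might also infer that 9.2.6 contradicts 9.1. It does not do so literally: the list withdraws subjects from the study, later treatment is left to the investigator's clinical judgment, and 9.1 itself foresees early end of participation. Mandatory removal, partly in consultation with the sponsor's monitor, sits uneasily with a non-interventional design, but that is a tension.

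**Conclusion.** The point holds in a limited form. On the text, a patient still taking adalimumab can be withdrawn under 9.2.6, has no category in 12.6, and belongs to neither analysis population. The mismatch with 12.6 is direct and needs no assumption about rates.

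The bias is conditional. It arises only for patients withdrawn on drug, and only if their HAQ-DI change is worse. Its formula is k × d. The 0.006 to 0.05 range (2.9% to 23.8% of the planned -0.21) is an illustration from assumed inputs and should not be read as an estimate. The planned power is not in question.

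Prohibited medications are mentioned in 9.2.6 and 9.8.2 without a list in the text available. That is missing detail and gives no support to the bias argument. Overall this is a cheap improvement worth making. It does not invalidate the primary test.

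**What to change.** 1. **Reconcile the passages.** Bring 9.2.6, 12.6 and the deviation list in 9.8.2 into line, together with the pregnancy wording in 9.2.4.5 and 11.1.6, which repeats one of the 9.2.6 grounds. No position is taken here on when adalimumab should be stopped.
2. **Separate two events.** Record stopping adalimumab and leaving data collection as different things. Patients who remain on adalimumab under their physician and still consent keep their Week 12 and Week 24 questionnaires and stay in the as-observed population, with the triggering event recorded.
3. **Assign populations in the SAP.** State in 2.1, 2.3 and 5.3 which population each withdrawn patient belongs to, so that each falls into exactly one, and report withdrawals by reason.
4. **Add a sensitivity analysis** of the Week 24 change that uses the early-termination HAQ-DI already listed in Table 1.
5. **Tidy the wording.** List the prohibited medications or delete the references to them.

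The cost is wording changes in the protocol and the SAP, one extra analysis, and a few more questionnaires at routine visits.

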9.7 Data Analysis

9.7.1 Statistical and Analytic plans

A statistical analysis plan (SAP) will be developed describing the specific analysis that will be performed including, and in addition to, the analysis described here. All analysis will be performed in accordance with the approved analysis plan. The following provides an overview of some of the analysis.

The scoring of the PRO questionnaires will be done in accordance to the developers' recommendations.

A separate statistical analysis plan will be developed describing the specific analysis that will be performed including and in addition to the analysis described here.

9.7.2 Analyzable population

All subjects who received at least one dose of adalimumab during the study will be included.

9.7.3 Planned Methods of Statistical Analysis

All statistical tests will be two-tailed with a significance level of 0.05. Descriptive statistics will be provided. Descriptive analysis will be conducted on all key parameters and presented as mean, standard deviation, minimum, maximum, and median when continuous and as "n" and percent when categorical. Change from adalimumab initiation to 24 weeks will be calculated and evaluated for significant improvements using paired t-tests / ANOVA for parametric and Wilcoxon signed-rank for non-parametric data. Analysis will be also be conducted by severity level (moderate vs severe), disease duration quartile (to compare to prior work) and up to two (2) other subgroups. Cochran-Armitage test of trends or other similar methods may be used to compare categories of subjects.

9.7.4 Primary Endpoint Analysis

The primary endpoint variable will be the change in HAQ DI score at 24 weeks after the initiation of adalimumab, in those patients continuing on adalimumab (as observed population).

The objective of the primary endpoint analysis will be to demonstrate that treatment with adalimumab improves functioning as measured by the HAQ DI in subjects with RA following treatment initiation. This change will be summarized as the mean and 95% confidence interval and will be tested with a paired t-test without adjusting for baseline disease severity. For sensitivity analysis, the mean change in HAQ DI at Week 24 will be analyzed using ANOVA adjusting for baseline disease severity.

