9.7.5 Secondary Endpoint Analysis

The main secondary endpoint variable will be the change in HAQ DI at 12 weeks after the initiation of adalimumab.

The objective of endpoint analysis will be to demonstrate that treatment with adalimumab improves functioning as measured by HAQ DI in subjects with RA compared to baseline.

The main secondary analysis will be summarized as the mean and 95% confidence interval and will be tested with a paired t-test without adjusting for baseline disease severity. For sensitivity analysis, the mean change in HAQ DI at Week 12 will be analyzed using ANOVA adjusting for baseline disease severity.

Other secondary analyses include:

- Change in other patient reported outcomes (SF-36 domain scales, EQ-5D Index, WPAI total lost productivity) at weeks 12 and 24 after the initiation of adalimumab, in those patients continuing on adalimumab (as observed population). These changes will be summarized as the means and 95% confidence intervals and will be tested with paired t-tests.
- Number and percent of patients achieving a clinically meaningful improvement on the HAQ DI, as defined by a -0.22 point improvement or greater, at weeks 12 and 24 after the initiation of adalimumab, in those patients continuing on adalimumab (as observed population).

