2.1 Primary Objectives

- To describe the change in HAQ DI score at 24 weeks after the initiation of adalimumab (i.e. baseline), in those patients continuing on adalimumab (as observed population). This change will be summarized as the mean and 95%

confidence interval and will be tested with a paired t-test without adjusting for baseline disease severity. For sensitivity analysis, the mean change in HAQ DI at Week 24 will be analyzed using ANOVA adjusting for baseline disease severity.

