3.5.5 Conventions

Given the real world nature of the data, multiple imputation methods for missing data will introduce bias as missing data cannot be considered completely at random (MCAR) or at random (MAR). Due to the observational nature of this study, non-imputing process will be applied, except with date data where the exact day is missing; day “15” will be assumed. Efficacy measures are not assessed after a participant discontinues adalimumab. The exception to this will be the analysis of proportion of patients at 24 weeks who remain on adalimumab. Item level data on the PROs will be imputed according to the developers’ recommendations. Therefore, the analysis will be based on available data. The number of patients with missing data for each variable will be summarized and reported.

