5.3 Analysis Plan for Primary Objectives

The objective of the primary endpoint analysis will be to demonstrate that treatment with adalimumab improves functioning as measured by the HAQ DI score in subjects with RA following treatment initiation (i.e. baseline).

- The changes in HAQ DI score at 12 and 24 weeks after the initiation of adalimumab will be presented (Excel Table 3.1); these changes will be summarized as the mean, SD, minimum, maximum, median, 95% confidence interval; as well as the number and percent of patients achieving a clinically meaningful improvement on the HAQ DI, as defined by a -0.22 point improvement or greater. In addition, the mean change will be tested with a paired t-test without adjusting for baseline disease severity, shown by p-value1; for sensitivity analysis, the mean change will be analyzed using ANOVA adjusting for baseline disease severity, shown by p-value2 in the table.
- The change in HAQ DI score at 24 weeks after the initiation of adalimumab (mean, SD, minimum, maximum, median, 95% confidence interval), in those patients continuing on adalimumab (observed population) will be compared with those patients not continuing on adalimumab (withdrawal population). The mean changes in these two groups will be compared using an independent t-test with p-value listed in the table (Excel Table 3.2).

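### HAQ-DI change and responder results are planned only for patients who stay on adalimumab, with no all-treated supplement, and the Table 3.2 test needs a week-24 score that withdrawn patients do not have

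*Protocol*

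**What the plan says.** Protocol 9.7.4 defines the primary variable as the "change in HAQ DI score at 24 weeks after the initiation of adalimumab, in those patients continuing on adalimumab (as observed population"). SAP 2.1 repeats the restriction: "in those patients continuing on adalimumab (as observed population"). The responder count, "as defined by a -0.22 point improvement or greater, at weeks 12 and 24 after the initiation of adalimumab", is limited in the same way in Protocol 9.7.5 and SAP 2.2.

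The aim in SAP 5.3 is wider: "to demonstrate that treatment with adalimumab improves functioning as measured by the HAQ DI score in subjects with RA following treatment initiation". Protocol 9.7.2 defines the analysable population as everyone dosed: "All subjects who received at least one dose of adalimumab during the study will be included". No HAQ-DI summary is assigned to that set.

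On missing data, SAP 3.5.5 states that "multiple imputation methods for missing data will introduce bias as missing data cannot be considered completely at random (MCAR) or at random (MAR"), and it uses available data. The only imputation is for questionnaire items and partial dates. It also says: "The number of patients with missing data for each variable will be summarized and reported". The one sensitivity analysis for HAQ-DI change is an ANOVA adjusting for baseline severity.

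Protocol 9.7.6 and SAP 5.3 (Table 3.2) compare the 24-week change in continuing and withdrawn patients by an independent t-test. Protocol Table 1 (9.1.1) schedules the HAQ at early termination, and 9.2.6 places that assessment within 2 weeks of the last dose. Protocol 9.7.9 says efficacy is not assessed once adalimumab is stopped. Section 12.6 makes stopping the drug a study drop-out, after which nothing more is collected except the reason.

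**The concern.** There are two separate issues.

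First, the as-observed figures describe patients who remained on drug, while the objective speaks of the effect of starting it. The SAP itself regards missingness as informative. An available-data analysis is exposed to that problem just as imputation is, yet nothing planned shows how far the result could move. The ANOVA changes the model but not the patients. What is at stake is the size of the effect and the responder percentage that a payer would read as applying to all starters.

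Second, Table 3.2 cannot be run as written. By design a withdrawn patient has no week-24 HAQ-DI. What may exist is a termination score and, for those who left after week 12, a week-12 score. No rule says which is used or how its earlier timing is handled, so two programmers could produce different tables.

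**Working it through.** **Which HAQ-DI scores exist**

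- Continuing patients: baseline, week 12 and week 24 (Protocol Table 1).
- Withdrawn patients: baseline, week 12 if they left later than that, and a termination score within 2 weeks of the last dose (Table 1 and 9.2.6).
- Patients still on drug who missed a questionnaire: Protocol 12.6 says they are not drop-outs.

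Read strictly, 9.7.9 and 12.6 would leave the withdrawal group of Table 3.2 with no usable outcome. Read with Table 1 and 9.2.6, they leave scores taken at varying times before week 24.

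**Inputs**

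- Protocol 9.5: 100 patients, 10% dropout, two-sided 0.05; mean change -0.21 with SD 0.5, and mean -0.5 with SD 0.7.
- SAP 4: dropout 13%, range 10-15%.
- Assumptions made here: these means and SDs hold in continuers, and changes are normally distributed. Neither document gives outcomes for leavers.

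**The plan's own power figures** (paired t-test, noncentral t, n = 100 × 0.90 = 90)

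- Mean -0.21, SD 0.5, against 0: 97.6%. Stated: at least 95%. Reproduced.
- Mean -0.5 against -0.22, a difference of 0.28, SD 0.7: 96.4%. Stated: at least 95%. Reproduced.

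**Responders.** Rate in continuers = Φ((-0.22 - m)/s). The all-treated rate, with withdrawals counted as non-response, is (1 - d) times that.

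- m = -0.50, s = 0.7: Φ(0.40) = 65.5%.
- m = -0.21, s = 0.5: Φ(-0.02) = 49.2%.

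| Dropout d | m = -0.50, s = 0.7 | m = -0.21, s = 0.5 |
|---|---|---|
| 10% | 59.0% | 44.3% |
| 13% | 57.0% | 42.8% |
| 15% | 55.7% | 41.8% |

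The fall is 6.6 to 9.8 points in the first case and 4.9 to 7.4 in the second.

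**Mean change.** All-treated mean = (1 - d)m + d·f·m, where f is the fraction of the continuers' benefit that leavers have. The two values in each cell are for d = 10% and d = 15%.

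| f | m = -0.50 | m = -0.21 |
|---|---|---|
| 0 | -0.450, -0.425 | -0.189, -0.179 |
| 0.5 | -0.475, -0.463 | -0.200, -0.194 |
| 1 | unchanged | unchanged |

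**Significance against zero** (m = -0.21, s = 0.5, all 100 treated, d = 10% then 15%)

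- Every leaver has exactly zero change: SD = √((1-d)(s²+m²) - ((1-d)m)²) = 0.479, 0.467; power 97.4%, 96.6%.
- Leavers average zero with SD 0.5: SD = √(s²+d(1-d)m²) = 0.504, 0.506; power 96.0%, 93.8%.
- Leavers worsen by 0.21 on average: power 89.7%, 79.6%.

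**Table 3.2 precision.** Half-width = t(0.975, 98) × s × √(1/n1 + 1/n2), with t = 1.984 and every withdrawn patient supplying a score.

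| Continuing v withdrawn | s = 0.5 | s = 0.7 |
|---|---|---|
| 90 v 10 | 0.33 | 0.46 |
| 87 v 13 | 0.30 | 0.41 |
| 85 v 15 | 0.28 | 0.39 |

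Each is wider than the 0.22 that the plan treats as clinically meaningful. Any missing termination score widens it further.

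**The case against.** The strongest reply is that the plan makes no error here. The as-observed population is declared in the abstract, the protocol body and the SAP. The objective itself speaks of data as observed, and in a single-arm observational study a further summary is a matter of preference. That the restriction is open and legitimate stands. It does not answer why an aim about treatment initiation has no summary of everyone who initiated.

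It can also be said that Protocol 9.7.2 includes all dosed patients and that the Table 3.1 bullet in SAP 5.3 names no population. That is ambiguity, but the objectives the table serves (SAP 2.1, 2.2) point back to continuers, so no all-treated summary is planned.

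Leavers are not hidden: Table 3.2 describes them, and missing counts will be reported. But Table 3.2 plans no responder percentage, and its means depend on the missing rule. The comparison is exploratory, so no primary or secondary claim rests on it. That limits the weight of the second issue.

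The illustration is hypothetical. HAQ-DI with eight categories answered moves in steps of 1/8 = 0.125, so the cut-off is in effect -0.25. A continuity correction raises the continuers' rates to about 67% and 52%. The proportional fall of 10-15% is unaffected.

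A reader might infer more than the documents support:

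- **That leavers necessarily do worse.** No outcomes are given, some leave for reasons other than poor response, and patients thought unlikely to adhere are excluded at entry (Protocol 9.2.2).
- **That the Early Termination Form leaves a gap.** The drop-out situation it does not cover is patients who cannot be contacted.
- **That retention on drug goes unreported.** SAP 3.5.5 names it: "The exception to this will be the analysis of proportion of patients at 24 weeks who remain on adalimumab". The full table shells are a separate workbook not available here, so its absence from the table list shows little.

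**Conclusion.** The point holds in two limited parts and should be fixed.

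The as-observed analysis is sound for patients who remain on adalimumab. Read as a result for all starters, it is likely, though not certainly, too favourable. Under the assumptions above, the responder rate would be about 5 to 10 percentage points lower with withdrawals counted as non-response. The mean change would be between 0% and 15% smaller if leavers keep between all and none of the benefit, and smaller still if they worsen.

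It would be wrong to conclude that the stated power is mistaken or that the primary test is in doubt. Both HAQ-DI power figures reproduce, and the test against zero keeps about 94% power or more if leavers average no change. It drops to 80-90% only if they worsen by as much as continuers improve.

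Table 3.2 is unworkable as a week-24 comparison. Even with a score from every leaver it could not settle a difference of 0.22.

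**What to change.** 1. Keep the as-observed primary analysis and label it as applying to patients who remained on adalimumab.
2. Add to SAP 5.3 and Table 3.1 a supplementary all-treated responder percentage at weeks 12 and 24, with withdrawals counted as non-response. Show on-drug patients who only missed a questionnaire separately, since Protocol 12.6 does not class them as drop-outs. If an all-treated mean change is also shown, use the termination HAQ-DI where there is one. Carry baseline forward only as a labelled reference value for leavers with no score.
3. Redefine Table 3.2 for withdrawn patients as a descriptive change from baseline to termination, with the number and timing of scores, and drop the week-24 t-test.
4. Reconcile Protocol 9.7.9 and 12.6 with Table 1 and 9.2.6, so that it is clear that the termination assessment is collected and used.

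The cost is a few table rows, some wording, and a slightly less favourable supplementary estimate. No new data are needed. Database lock was planned for 28 February 2017 (Protocol 6.0), and the SAP cites table shells dated January 2018. If lock has passed, the additions must be labelled post hoc.
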